#### 6. Study Design

#### 6.1. Duration

Including enrollment and follow up time, the current study is estimated to progress for up to 18 months. During this time, subjects will participate for a maximum of 67 days. Subject screening for

MDT17024BZP

Version 5.0 (18 MAR 2019)

Page 15 of 47

Medtronic

eligibility will occur up to 30 days prior to the procedure. Post-procedure, subjects will be assessed for pain and their ability to return to normal diet and activity via a patient diary and either the FLACC behavioral pain assessment scale (age 2) or the Wong Baker Faces® Scale at days 1 through 7, Day 10 (+/-1 day), Day 14 (+/-1 day), and Day 28 (+/-1 day), before returning the FLACC/FACES® scales and Patient Diary during the return to clinic on day 28 (+7). Please see section 9 for study schematic.

#### 6.2. Rationale

In order to assess the clinical safety and performance of BiZact™ (BZ4212) on a pediatric population, Medtronic is performing a prospective, multi-center, single arm study of BiZact™ on children (2-12 years of age at the time of the procedure, inclusive) undergoing tonsillectomy. Intra-operative blood loss will be assessed as well as post-operative pain and other quality of life aspects for 28 (+7) days following the procedure. Pre-clinical testing has found BiZact™ to satisfactorily achieve hemostasis and currently a multicenter adult tonsillectomy study is underway in the US and Europe. As a study with no comparator, this study does not utilize any randomization or blinding. The BiZact™ device will only be used during the course of the tonsillectomy procedure and subjects will be followed for 28 (+7) days to monitor bleeding, pain and return to normal diet and activity. If any adverse events are identified they will be assessed, reported and documented in the eCRF.

#### 7. Product Description

#### 7.1. General

The BiZact™ is a single use bipolar electrosurgical instrument intended for use in general open surgical procedures. It is also indicated for adult ENT procedures, including tonsillectomy, for the ligation and division of vessels, tissue bundles, and lymphatics 2-3 mm away from unintended thermally sensitive structures.

BiZact™ is a pistol grip RF-based sealer/ dissector similar (design, technology and materials) to current Ligasure™ devices. Akin the commercialized device, LF1212 (Ligasure™ small jaw), BiZact™ includes a jaw, a deploying knife, a lever to open and close the jaws, and a trigger to deploy the knife and inline activation of bipolar energy. The device does not include a rotation knob for rotating the jaws, but the device does allow surgeons to perform procedures by switching hands. BiZact™ is compatible with the Valleylab™ (LS10 with V1.1 or V1.2 software, ForceTriad with v4.0 software, and FT10 with v2.0 software) energy platforms, which are able to recognize the device utilizing radiofrequency identification (RFID) or barcode capabilities. In total, 120 BiZact™ units will be assigned to this study to account for any situations in which more than one device is needed.

# BiZact™ Pediatric Clinical Study Protocol MDT17024BZP Version 5.0 (18 MAR 2019) Page 16 of 47 Medtronic

[figure not shown]

Figure 1: BiZact™ (BZ4212) schematic diagram (left), and device photo (right)

#### 7.2. Dosage Form and Route of Administration

This instrument creates tissue fusion by application of bipolar electrosurgical RF energy and pressure to vessels/tissue interposed between the jaws of the instrument. The tissue fusion can then be transected using the built in cutting mechanism. The instrument can be used for vessels and lymphatic tissue up to and including 3mm in diameter and tissue bundles. The instrument also incorporates inline RF activation, features for grasping and tips for dissection. The instrument is intended primarily for surgeons performing tonsillectomies. See Instructions for Use (included in Appendix A) for instructional information.

The BiZact™ device has received the following approvals for the ligation and division of vessels, tissue bundles and lymphatics 2-3 mm away from unintended thermally sensitive structures;

- Food and Drug Administration (FDA) indication for adult ENT procedures including tonsillectomy (US)
- Therapeutic Goods Administration (TGA) License for ENT procedures including tonsillectomy in adults, children and adolescents (AUS)

This information is contained in the IFU (Appendix A) but the IFU accompanying the device should always be consulted.

#### 7.3. Manufacturer

BiZact™ is manufactured by Covidien (Covidien LP is an indirect wholly owned subsidiary of Medtronic plc.). The Covidien facility located at [name] is an FDA registered establishment (1717344) manufacturing US Class 1 and 2 medical devices in accordance with the 21 CFR 820 Quality System Regulation. The site also holds both an ISO 13485 Quality Management Certificate (FM 71825) and Full Quality Assurance System Certificate (CE 00500). Both certificates are issued by Boulder's Notified Body, BSI. BSI holds annual quality assessments to ensure continued compliance to quality processes.

MDT17024BZP

Version 5.0 (18 MAR 2019)

Page 17 of 47

Medtronic

Components used in the assembly of the device are manufactured by several different suppliers. All suppliers undergo a robust qualification process prior to inclusion on Covidien's "Approved Supplier List." Once suppliers are selected, they are audited on a periodic basis per Covidien's procedures to ensure continued adherence to Covidien specifications and standards. Each supplier is assigned a risk rating, and this determines the timetable for subsequent audits that are not for cause.

#### 7.4. Packaging

See Appendix A, Instructions for Use. BiZact™ is provided as a single use disposable product. Each instrument is individually packaged and sealed in a Tyvek® pouch. Six sealed pouches are packaged in one shipper case.

In the United States, the BiZact™ devices will be labeled as investigational according to regulations: "CAUTION – Investigational Device - Limited by Federal (or United States) Law to Investigational Use."

For Australia, devices for the study will be shipped accompanied by instructions that the devices are indicated for the BiZact™ clinical study use only, to be used by study qualified investigators, and consistent with local requirements.

#### 7.5. Intended Population

The BiZact™ device has received the following approvals or clearances for the ligation and division of vessels, tissue bundles and lymphatics 2-3 mm away from unintended thermally sensitive structures;

- Food and Drug Administration (FDA) indication for adult ENT procedures including tonsillectomy (US)
- Therapeutic Goods Administration (TGA) License for ENT procedures including tonsillectomy in adults, children and adolescents (AUS)
- CE Mark under the Medical Device Directive for use in ENT procedures including tonsillectomy in adults, children and adolescents (EU)

#### 7.6. Equipment

BiZact™ devices are single-use disposable products. If needed, a compatible Valleylab™ generator will be supplied and approved by the hospital biomedical department if applicable. Each site will receive or be assigned to use a different compatible Valleylab generator for this study. BiZact™ is compatible with the Valleylab™ (LS10 with V1.1 or V1.2 software, ForceTriad with v4.0 software, and FT10 with v2.0 software) energy platforms, which are able to recognize the device utilizing radiofrequency identification (RFID) or barcode capabilities after the BiZact™ device is plugged into the Ligasure ™ port of the Valleylab generator. There is no need for any necessary calibration or monitoring of the equipment to enable use with the BiZact™ device.

#### 7.7. Product Use

The BiZact™ device is a bipolar electrosurgical instrument intended for use in open surgical procedures where ligation and division of vessels, tissue bundles, and lymphatics is desired.

MDT17024BZP

Version 5.0 (18 MAR 2019)

Page 18 of 47

Medtronic

The tissue fusion function of the device can be used on vessels (arteries and veins) and lymphatics up to and including 3 mm diameter. The BiZact™ device is indicated for use in open general surgical procedures.

The BiZact™ device has not been shown to be effective for tubal sterilization or tubal coagulation for sterilization procedures, and should not be used for these procedures.

This information is contained in the IFU (Appendix A) but the IFU accompanying the device should always be consulted.

#### 7.8. Product Training Requirements

Each Investigator participating in the clinical study and the associated clinical study staff will receive training on the clinical protocol, as well as the BiZact™ device. Investigators and study staff will be trained on device characteristics, shelf life and storage requirements, device use, and warnings, precautions, contraindications.

#### 7.9. Product Receipt and Tracking

BiZact™ will be shipped to each site with the shipment form (which includes shipping/ dispersal date, the quantity, model, lot, and, serial number and expiration date). Each site will review contents and document on the form the confirmation the shipment information is accurate as well as the date received. The use of the device for a procedure or disposition of the devices (e.g. if returned due to damage upon arrival) will be recorded in the eCRF device tracking section in conjunction with the above information.

BiZact™ will be provided to each site upon Sponsor collection and approval of all required regulatory documentation. Additionally, a Valleylab™ generator will be supplied if necessary (see above).

#### 7.10.Product Storage

Access should be limited to designated study staff only. Study devices should be kept in an area or otherwise contained where only qualified study personnel can access the device (i.e. locked or secured). This area/container should be kept at ambient temperatures without exposure to water with adequate provisions for maintaining ambient temperatures if a loss of power is experienced. Device accountability will be tracked in the electronic case report forms (eCRFs). If the devices are exposed to water or a drastic change in temperature, sites should contact the study team for possible replacement devices.

#### 7.11. Product Return

It is the responsibility of the site to return the Valleylab™ generator to Medtronic within 30 days of the End of Study if one was loaned, along with any unused or expired BiZact™ devices. Sites should follow instructions and complete all appropriate forms provided by the study team for product return.

#### 7.12. Product Accountability

Access should be limited to designated study staff only. Device accountability will be tracked in the electronic case report forms (eCRFs). It is the site's responsibility to document the receipt (which

MDT17024BZP

Version 5.0 (18 MAR 2019)

Page 19 of 47

Medtronic

includes shipping/ dispersal date, the quantity, model, lot, and, serial number and expiration date), disposition of the product (per subject use, including amount used, amount remaining, etc.), transfer (if applicable) and return of all unopened investigational medical devices.

## 8. Selection of Subjects

#### 8.1. Study Population

A minimum of sixty (60) completed procedures with subjects ages 2-12 (at the time of the procedure inclusive), with at least 40% study wide in the age range of 2-5 years of age, will be undertaken at a minimum of 2 sites in US. When 36 procedures with subjects ≥6 years of age have been completed (60% of minimum total enrollment), enrollment for this age group will close. A minimum of five surgeons across the 2 sites will participate.

The sample size of 60 was selected to ensure that multiple surgeons participate and to create an opportunity for a range of subject ages to be enrolled. Power considerations are detailed below (Section 13).

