## 8.2. Subject Enrollment

A minimum of 60 subjects will be enrolled in the study at a minimum 2 sites with competitive enrollment not to exceed 36 enrolled subjects per site. Subjects' participation in the study will last 28 (+7) days post procedure. Subjects will be considered for the study if they meet all of the preoperative inclusion criteria and none of the exclusion criteria (Section 8.3, 8.4), and sign the informed consent form.

A subject is considered enrolled in the study when the subject's legally authorized representative signs the informed consent form. However, data will not be collected for the study until the subject has determined to be eligible for the study and the surgical procedure has begun. No adverse event information will be recorded before the procedure has begun. As soon as the tonsillectomy procedure has begun and the study device has contacted the patient, the patient must be followed regardless of whether or not the procedure has been fully completed with the device . See section 9.10.3 for the full definition of enrolled subjects. The procedure will be performed per the institution's standard practice.

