#### 9.10.3. Enrolled Subjects

A subject is considered enrolled in the study when the subject's LAR signs the consent. Data will not be captured until the subject is determined to be eligible and the tonsillectomy has begun (Day 0). As soon as the tonsillectomy surgical procedure has begun and the BiZactTM device has been in contact with the subject, the subject must be followed. Subjects who are enrolled, but discontinue the study for any reason prior to the start of the tonsillectomy procedure or usage of the study device, will not be followed unless they are later able to complete the tonsillectomy, See section 9.10.4. These subjects will not count towards the 60-subject enrollment for the study, nor towards the site enrollment maximum (36). In all subject cases where the device was in contact with the subject will be included in the intent-to-treat (ITT) population. The per-protocol population will consist of subjects in the ITT population that did not have a major protocol deviation.

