## 13.8. Poolability of Results

Poolability of blood loss data will be assessed for each of the participating investigational sites. Descriptive statistics will be reported separately by site. A one-way ANOVA will test whether there is evidence of a difference in mean blood loss between sites. If this test does not suggest a difference (p-value  $\geq 0.15$ ), data will be pooled across sites for inference (i.e., for the primary hypothesis test and 95% confidence interval for mean blood loss). If there is evidence of a difference (p < 0.15 from the one-way ANOVA), confidence intervals will be presented separately for each site, and p-values from the hypothesis test in Section 8.4.1 will also be calculated separately for each site. For full details on the planned analysis and poolability, see Statistical Analysis Plan (SAP).

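### The pooling test in 13.8 has no age term, so if sites enrol different age mixes and blood loss depends on age, it cannot tell an age-mix difference from a site difference

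*Combined protocol and SAP*

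**What the plan says.** Protocol 8.1 requires a minimum of 60 completed procedures, "with at least 40% study wide in the age range of 2-5 years of age". The closing rule for the older group is also study-wide: "When 36 procedures with subjects ≥6 years of age have been completed (60% of minimum total enrollment), enrollment for this age group will close".

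Protocol 8.2 allows the study to run at as few as two sites. Its only limit on what any one of them may recruit is a ceiling on the count: "competitive enrollment not to exceed 36 enrolled subjects per site". No age condition is attached to a site. Section 8.1 adds a surgeon minimum ("A minimum of five surgeons across the 2 sites will participate"), also without reference to age.

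Protocol 13.8 governs pooling: "A one-way ANOVA will test whether there is evidence of a difference in mean blood loss between sites". At p of 0.15 or more, the sites are pooled for the primary test and its confidence interval. Otherwise, "If there is evidence of a difference (p < 0.15 from the one-way ANOVA), confidence intervals will be presented separately for each site", and the primary p-value is also calculated by site. The section refers to the SAP for full details.

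Protocol 13.4.1 plans descriptive blood loss summaries by age group (2-5 and 6-12), site, surgeon and country. It does not mention age group within site.

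**The concern.** The protocol treats age as a design factor: it has a quota, a closing rule and planned age-group summaries. The pooling test nevertheless ignores age, and nothing in the enrolment rules keeps the age mix similar across sites.

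If older and younger children bleed by different amounts, a difference in age mix shifts the site means even when children of the same age bleed equally at both sites. The test may then report a site difference that is really one of case mix. The reverse is also possible: an age-mix difference could hide a true site difference.

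What is at stake is whether results are presented pooled or by site, and how a site difference is explained. Summaries taken one factor at a time would not show the source.

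**Working it through.** **Inputs from the documents.** Goal 31 mL, expected mean 10 mL, SD 15.1 mL (13.4.1); one-sided alpha 0.025 and n = 60 (13.2); age rules (8.1); site cap (8.2); pooling threshold 0.15 (13.8).

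**Assumptions.** Blood loss differs by D mL between ages 6-12 and 2-5, with D = 5 or 10 as the main cases. There is no true site effect. Errors are normal with SD 15.1. The two sites have 36 and 24 subjects.

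**1. The plan's own figure.** The noncentrality of the one-sample t-test is (31 − 10)/15.1 × √60 = 10.77. Power exceeds 0.9999, which agrees with the stated value above 99%. For one site alone, noncentrality is 21/15.1 × √24 = 6.81 and 21/15.1 × √36 = 8.34; power exceeds 0.9999 in both cases. At a true mean of 15 mL and n = 24 it is still 0.998 or more.

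**2. What enrolment allows.** 0.40 × 60 = 24 and 0.60 × 60 = 36. Site A with 36 older children and site B with 24 younger ones gives 60 subjects, 24/60 = 40% aged 2-5, and breaks no cap. Any less extreme mix with no more than 36 older children in total is also allowed.

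**3. Chance of a site flag.** Let fA and fB be the fractions of older children at each site. The site means then differ by δ = D × (fA − fB). The two-group ANOVA has noncentrality

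λ = δ² / [15.1² × (1/36 + 1/24)] = δ² / (228.01 × 0.06944) = δ² / 15.83,

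and flags when F(1, 58) exceeds 2.128.

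| Older at A, B | fA − fB | D (mL) | δ (mL) | λ | P(flag), formula | P(flag), simulated |
|---|---|---|---|---|---|---|
| 36/36, 0/24 | 1.000 | 5 | 5.00 | 1.579 | 0.427 | 0.426 |
| 36/36, 0/24 | 1.000 | 10 | 10.00 | 6.316 | 0.853 | 0.853 |
| 30/36, 6/24 | 0.583 | 5 | 2.92 | 0.537 | 0.253 | 0.249 |
| 30/36, 6/24 | 0.583 | 10 | 5.83 | 2.149 | 0.507 | 0.488 |
| 24/36, 12/24 | 0.167 | 5 | 0.83 | 0.044 | 0.159 | 0.154 |
| 24/36, 12/24 | 0.167 | 10 | 1.67 | 0.175 | 0.185 | 0.166 |

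The simulation (100,000 trials per row) is the better guide in the mixed cases. There the age difference also adds spread within a site, which the formula leaves out.

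For smaller age differences the complete split gives 0.20 (2 mL) and 0.26 (3 mL). With D = 0 the rate is 0.15 for every mix.

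**4. With age group in the model.** The simulated flag rate for site returns to 0.15 in both mixed cases at 5 and 10 mL. In the complete split the site and age columns are identical (design matrix of rank 2 with 3 columns), so no model can estimate both effects.

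**The case against.** The case on the other side is substantial, and most of it stands.

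- **Permitted is not likely.** Both sites recruit ages 2-12, and nothing suggests that either specialises by age. With a moderate imbalance the distortion is negligible. This stands.
- **The age effect is assumed.** Differences of 5 to 10 mL are 50% to 100% of the expected mean of 10 mL. This stands; with no age effect there is no problem.
- **The SAP was not available.** Section 13.8 defers details to it, so it may already contain an age term. This stands as a limit on the point, although the rule printed in 13.8 has none.
- **Three sites.** Section 12 still mentions 3 sites. A third site would lessen the possibility without removing it.

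A reader might also infer more than the documents support:

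- *That the matching caps of 36 create the problem.* They do not. Complete separation is possible at any two-site split of 60 from 24/36 to 36/24, and partial imbalance needs no cap at all.
- *That the site test would simply measure age.* In the complete split it measures age, site, surgeon and generator together (7.6 assigns each site a different generator). The effects cannot be separated, but none of them is shown to dominate.
- *That age will follow surgeons' experience with the device.* Both age groups are open until the older one closes, and nothing makes them sequential.
- *That the primary conclusion is in danger.* At the planning values each site alone has power above 0.9999.

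**Conclusion.** The point holds in a limited form. The pooling rule printed in 13.8 cannot distinguish a difference in age mix from a difference between sites, and the enrolment rules do not keep age mixes alike.

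With SD 15.1 mL, no true site effect and assumed age differences of 5 and 10 mL, the flag rate rises from 0.15 to about 0.25 and 0.49 under strong imbalance. It rises to 0.43 and 0.85 in the complete split, which is permitted but unlikely. Under moderate imbalance it stays at about 0.15 to 0.17.

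The harm is to the pooling decision and its interpretation. It depends on an age effect that the documents do not quantify, and on the SAP not already adjusting for age.

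**What to change.** In 13.8, replace the one-way ANOVA with a two-factor model. Suggested wording: *Differences between sites will be tested in a linear model for blood loss with site and age group (2-5, 6-12 years) as factors, using the same 0.15 threshold for the site term. Blood loss will also be summarised by age group within site. If the age groups are completely separated by site, the report will state that the two effects cannot be distinguished.* If the SAP already does this, bring 13.8 into line with it.

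**Cost.** One model term and one table, from data already collected, plus the review that 15.6 requires if the change is made as a protocol amendment. The adjusted site test is somewhat less sensitive when the mixes differ strongly. For 30/36 versus 6/24 the squared correlation of site and age is 0.583² = 0.34, so the standard error of the site difference grows by √(1/0.66) = 1.23, from 3.98 to 4.90 mL. That loss reflects information the data do not contain.

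**Optional.** Minimum numbers per age group at each site would rule out complete separation, which no analysis can repair. They could also stall a small or late-opening site under competitive enrolment, so they are for the sponsor to weigh and are not required by this point.

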## 8.2. Subject Enrollment

A minimum of 60 subjects will be enrolled in the study at a minimum 2 sites with competitive enrollment not to exceed 36 enrolled subjects per site. Subjects' participation in the study will last 28 (+7) days post procedure. Subjects will be considered for the study if they meet all of the preoperative inclusion criteria and none of the exclusion criteria (Section 8.3, 8.4), and sign the informed consent form.

A subject is considered enrolled in the study when the subject's legally authorized representative signs the informed consent form. However, data will not be collected for the study until the subject has determined to be eligible for the study and the surgical procedure has begun. No adverse event information will be recorded before the procedure has begun. As soon as the tonsillectomy procedure has begun and the study device has contacted the patient, the patient must be followed regardless of whether or not the procedure has been fully completed with the device . See section 9.10.3 for the full definition of enrolled subjects. The procedure will be performed per the institution's standard practice.

